PROTOCOL TITLE: Gabapentin for pain control after osmotic dilator insertion and prior to D&E procedure: a randomized controlled trial

1) Protocol Title

Title: Gabapentin for pain control after osmotic dilator insertion and prior to D&E procedure: a randomized controlled trial

Protocol Version Date: 01/11/2018

2) Objectives

Pain management in the context of abortion is a topic that is both challenging and necessary to research. The Society of Family Planning (SFP 2014) lists it as a top research priority. Most research to date has focused on pain during the abortion procedure. One area that remains under investigated is women's pain experience during the time osmotic dilators are in the cervix prior to the dilation and evacuation procedure. As a result, management of pain during this time period varies greatly and is largely based on anecdotal experience. Adjunctive pain management with non-narcotic medications such as gabapentin may have a place during this time. Gabapentin is unique in that it is both well tolerated with minimal contraindications and low cost with 600 mg doses as low as \$0.24. Additionally, widespread dissemination of cell phones and text messaging now gives us the opportunity to communicate with women about their dilator-related pain experience in real-time, potentially improving data quality.

We have planned a randomized, controlled trial of repeated doses of gabapentin compared to placebo for pain management during the time after dilator insertion and prior to D&E the subsequent day. Participants will receive gabapentin 600 mg or placebo prior to dilator insertion. Pain scores will be measured via numeric rating scale (NRS) at baseline and 5 minutes after insertion while the participant is in clinic. Additional pain scores as well as side effect and additional analgesic use will be obtained by text message while the patient is at home at 2 hours, 4 hours, and 8 hours after time of dilator insertion. Final pain score, side effect, and analgesic use assessment will occur upon presentation to the pre-operative area for D&E. We hypothesize that women who receive gabapentin beginning at the time of dilator placement for a D&E procedure will report a smaller increase in pain from baseline at 8 hours after dilator placement compared to women receiving placebo.

3) Background

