3. Participant will be asked to provide pain level on 11-point (0-10) NRS immediately before study drug ingestion as the baseline pain score. Baseline symptoms (sedation and dizziness) will also be recorded.
4. Women will ingest the assigned gabapentin 600 mg or placebo
 - a. Stratified block randomization will occur to achieve even distribution of women based on vaginal parity (no prior vaginal delivery versus one or more prior vaginal deliveries). This strategy will ensure similar numbers of women with vaginal parity between gabapentin and placebo groups as this may be an important factor influencing pain with dilators in general.
 - b. A UC Davis Investigational Drug Services (IDS) pharmacist will use computer-generated randomization to place active or placebo treatment in two groups of sequentially numbered vials (to account for block randomization based on parity)
5. The physician will proceed with dilator insertion via our existing standardized method (including standard cervical anesthesia with 1% xylocaine 20 mL, standard number of dilators based on gestational age). Number of dilators and any pharmacologic means of cervical preparation are already reported in a standardized template and will be available for chart review.
6. Post-dilator pain will be assessed via NRS at five minutes after dilator insertion. Additional symptoms (sedation and dizziness) will be recorded.
7. Women will be discharged home with:
 - a. One additional study medication (Gabapentin 600 mg or placebo) to take at home 8 hours after the initial dose. This medication will be labeled by the IDS and completed by administering physician.
 - b. Standard prescriptions for acetaminophen 300 mg/codeine 30 mg and ibuprofen 800 mg to take as needed.
 - c. A reminder form that includes 24-hour research contact information, the times when they can expect text messages, a reminder to take the home dose of their assigned study medication at 8 hours after dilator insertion (exact time will be written out) and a reminder to bring the empty study medication bottle with them when they present for their procedure the next day.
 - d. Recommendation that they have a ride to and from abortion procedure the subsequent day.
8. Participants will be sent a baseline text message from the study phone prior to leaving the clinic. Participants will be encouraged to enable privacy features on their personal phone. Examples of security features will be reviewed and included in the consent.

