PROTOCOL TITLE: Gabapentin for pain control after osmotic dilator insertion and prior to D&E procedure: a randomized controlled trial

8) Data and/or Specimen Management and Confidentiality

Sample size calculation

For the purpose of calculating sample size, there is no existing data that truly mirrors the objective of this study (context of pain, use of NRS, and use of change in pain score from baseline). The closest approximation is the mean immediate post-dilator insertion pain score of 5.2 (SD 1.2) via NRS from Borgatta, et al (2012). However, when using this data point and a commonly cited clinically significant decrease in NRS pain score of 2 points, computation with SAS 9.1 (factoring in power at 80% ($\alpha=0.05$), normal distribution) yielded a small sample size of only 12 women per group. [27-33] Based on the block randomization there are four groups for a total of 48 women. To account for up to 20% of subjects not responding to text messaging for the primary outcome the sample size estimate will increase to 58 total women. To ensure we gather sufficient data to truly outline pain experience during the dilator-procedure interval, we will more than double the sample size to recruit 121 women. We will stratify these 121 women by presence or absence of prior vaginal parity. Ensuring similar distribution of vaginal parity between the gabapentin and placebo groups is important as vaginal parity may affect pain with osmotic dilators.

Statistical Analysis

We will use non-parametric testing to assess the primary outcome variable because we do not expect normal distribution of the data. Chi square analysis and fisher exact tests will be used to compare demographics and dichotomous variables as appropriate. I plan to describe the pain course for the total study cohort using means and medians as appropriate.

Data Management

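### The primary test of change from baseline is unnamed, with no baseline adjustment stated; naming a baseline-adjusted rank test guards against a possible loss of power at almost no cost

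*Combined protocol and SAP*

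**What the plan says.** The outcome has to be pieced together, because section 6 gives enrollment as the primary study endpoint. The hypothesis in section 2 is that treated women "will report a smaller increase in pain from baseline at 8 hours after dilator placement compared to women receiving placebo". The sample size paragraph in section 8 confirms the scale: it looks for prior data matching on "context of pain, use of NRS, and use of change in pain score from baseline" and finds none.

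Baseline is defined in section 7, step 3: "Participant will be asked to provide pain level on 11-point (0-10) NRS immediately before study drug ingestion as the baseline pain score". Steps 4 and 5, the study drug and then the cervical block and dilators, come afterwards.

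The only statement about the primary analysis is in section 8: "We will use non-parametric testing to assess the primary outcome variable because we do not expect normal distribution of the data". No test is named. Adjustment for baseline is neither planned nor ruled out.

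The sample size uses "a commonly cited clinically significant decrease in NRS pain score of 2 points" and a "mean immediate post-dilator insertion pain score of 5.2 (SD 1.2) via NRS" taken from another study.

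**The concern.** The natural reading of section 8 is a two-group rank test on the change scores. Subtracting baseline fixes its weight at 1. That weight is best only if one extra point at baseline predicts one extra point at 8 hours. Here baseline pain precedes the drug, the block and the dilators, while the 8-hour score measures pain with dilators in place, so a slope of exactly 1 cannot be taken for granted. Where the slope differs from 1, subtraction carries baseline noise into the comparison, and the trial is less likely to detect a real effect.

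The covariate that would prevent this is recorded for every participant. Leaving the test unnamed also leaves the choice open until the data are seen.

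**Working it through.** **Inputs from the documents.** Planned difference 2 points; SD 1.2; 80% power; alpha 0.05 (two-sided assumed); 121 recruited; up to 20% without an 8-hour reply. Evaluable: 121 × 0.8 = 96.8, or about 48 per arm with 1:1 allocation assumed.

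**Not in the documents.** Baseline SD, 8-hour SD, SD of change, and the correlation between baseline and 8 hours.

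**The plan's own figure.** n per group = 2(1.96 + 0.84)² × SD² / d².
- SD 1.2 used directly: 2 × 7.85 × 1.44 / 4 = 5.65, so 6 per group (7 by an exact t-test), not the stated 12.
- SD of change = 1.2 × √2 = 1.70 (equal SDs, zero correlation): 2 × 7.85 × 2.88 / 4 = 11.3, so 12. The protocol does not say it did this. 12 is also the two-arm total, 2 × 6.

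The SD assumed for the change score is therefore unstated.

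**Variance comparison.** Let s be the 8-hour SD, k = baseline SD / s, and r the correlation.
- Change score: s²(1 + k² − 2rk)
- Baseline-adjusted: s²(1 − r²)
- Difference: s²(k² − 2rk + r²) = s²(k − r)²

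This is never negative, and is zero only at k = r, which is a slope r/k of 1.

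**Power at the plan's SD.** With s = 1.2, difference 2 and 48 per arm, power exceeds 99.9% either way, even at k = 1, r = 0.

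**Power at an assumed 8-hour SD of 2.5**, 48 per arm, normal approximation: Φ(d / [SD × √(2/48)] − 1.96). Worked case, k = 0.8, r = 0, d = 2:
- Change: SD = 2.5 × √1.64 = 3.20, SE = 3.20 × 0.204 = 0.653, 2 / 0.653 − 1.96 = 1.10, power 86.4%.
- Adjusted: SE = 2.5 × 0.204 = 0.510, 2 / 0.510 − 1.96 = 1.96, power 97.5%.

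| k | r | Variance / s²: change, adjusted | d = 2: change, adjusted | d = 1.5: change, adjusted |
|---|---|---|---|---|
| 0.4 | 0 | 1.16, 1.00 | 95.3%, 97.5% | 77.9%, 83.6% |
| 0.4 | 0.2 | 1.00, 0.96 | 97.5%, 97.9% | 83.6%, 85.1% |
| 0.4 | 0.4 | 0.84, 0.84 | 99.0%, 99.0% | 89.4%, 89.4% |
| 0.8 | 0 | 1.64, 1.00 | 86.4%, 97.5% | 63.1%, 83.6% |
| 0.8 | 0.2 | 1.32, 0.96 | 92.7%, 97.9% | 72.5%, 85.1% |
| 0.8 | 0.4 | 1.00, 0.84 | 97.5%, 99.0% | 83.6%, 89.4% |
| 1.0 | 0 | 2.00, 1.00 | 79.1%, 97.5% | 54.7%, 83.6% |
| 1.0 | 0.2 | 1.60, 0.96 | 87.3%, 97.9% | 64.2%, 85.1% |

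For baseline SDs of 1 to 2 (k = 0.4 to 0.8) and r from 0 to 0.4, the loss is 0 to 11 points at d = 2 and 0 to 21 at d = 1.5. The corner k = 1, r = 0 goes further, to 18 and 29 points.

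**Check with the rank tests themselves.** Simulated scores were rounded and bounded at 0–10 (8-hour SD 2.5 before bounding, about 2.4 after), with 48 per arm and 4,000 runs per scenario. Each cell gives Wilcoxon on change, then rank ANCOVA.

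| Baseline SD after bounding | Underlying r | d = 2 | d = 1.5 |
|---|---|---|---|
| 0.7 (near zero) | 0.2 | 96.6%, 96.7% | 80.5%, 81.3% |
| 0.7 | 0.5 | 97.9%, 98.0% | 86.8%, 86.5% |
| 1.2 | 0.2 | 95.1%, 96.6% | 76.8%, 80.6% |
| 1.2 | 0.5 | 98.9%, 98.8% | 88.5%, 87.8% |
| about 2.25 | 0.2 | 85.3%, 97.0% | 62.1%, 81.2% |
| about 2.25 | 0.5 | 96.4%, 98.7% | 80.6%, 88.7% |

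Where rank ANCOVA trails, it does so by less than 1 point. In similar simulations with no true difference, type I error was about 5% for both.

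**The case against.** Four points can be made for the plan.

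- **Absence of adjustment is inferred from silence.** Rank ANCOVA is itself non-parametric, so section 8 does not exclude it. This stands: the plan leaves adjustment out without forbidding it.
- **The planned comparison is valid.** A reader might infer that it is biased, because a chance baseline imbalance of 0.5 with slope 0.3 moves the estimate by (1 − 0.3) × 0.5 = 0.35 points. Averaged over randomization there is no bias; the shift is the same loss of precision seen from inside one trial. With 48 per arm, an imbalance that large has a probability of about 1.4%, 10% or 22% at baseline SDs of 1, 1.5 and 2.
- **The loss may be nil.** Pain before any procedure may be low with little spread, which makes k small and can bring the slope close to 1. At k = 0.3, r = 0.3 nothing is lost. At the plan's SD of 1.2 nothing material is lost for any k up to 1. This stands as a possibility. The SD of 1.2, however, belongs to a score taken just after insertion in another study, and section 8 concedes that no prior data match this objective. Chronic pain is not an exclusion, so some baseline spread is possible.
- **Change from baseline was chosen deliberately.** Rewording the hypothesis late would be costly, since this version is dated 01/11/2018 and enrollment was due to end that month. This stands, and no rewording is needed.

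**Conclusion.** The point holds as a matter of efficiency. The outcome is change from a baseline taken before drug and dilators, and no baseline adjustment is stated. A raw change-score comparison is never more efficient in large samples than a baseline-adjusted one, and is less efficient whenever the slope is not 1.

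The size is conditional. Assuming an 8-hour SD of 2.5, 48 evaluable per arm and a baseline SD up to about 2, the loss is about 0 to 10 power points at the plan's 2-point difference and about 0 to 20 at 1.5 points. It is close to nil if baseline pain varies little, and larger only if baseline is as variable as 8-hour pain and nearly uncorrelated with it.

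A reader might go further and conclude that power is certainly lost, or that the trial falls short of its 80% target. The documents do not support either reading: they give no baseline SD and no correlation. At a 2-point difference, change-score power stays above 80% in every case shown except k = 1, r = 0, where it is 79.1%.

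**What to change.** In the Statistical Analysis paragraph of section 8, before unblinding, name the primary test: the 8-hour NRS score compared between arms by rank ANCOVA with baseline NRS as covariate. This keeps the non-parametric intent. Report change from baseline descriptively by arm. If a difference in NRS points is wanted, add a linear ANCOVA estimate.

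The hypothesis in section 2 can stay. In a linear ANCOVA with baseline as covariate, modelling the change or the 8-hour score gives the same between-arm coefficient, so the adjusted analysis still addresses the stated question.

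The cost is one sentence and one model term, with no new data and no extra participants. In the scenarios most favourable to change scores, rank ANCOVA gives up at most about 1 point of power.

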9. Participants will be contacted via text message at 2, 4, and 8 hours after dilator insertion.
 - a. Text messages will originate from a password protected study cell phone. Android application "SMS scheduler" will be used to send standardized text messages to the participant at pre-programed time intervals from time of dilator insertion.
 - b. Text message content:
 - i. Current NRS pain score
 - ii. Inventory of analgesic use since last contact
 - iii. Presence of symptoms (sedation and dizziness)

PROTOCOL TITLE: Gabapentin for pain control after osmotic dilator insertion and prior to D&E procedure: a randomized controlled trial

- iv. Reminder to take the assigned study medication (at 8 hours only)
10. Upon admission to the pre-operative ward prior to D&E, we will document the time and assess the current NRS pain score, additional analgesic use since 8 hour text message contact, and presence of symptoms (sedation and dizziness)

Blinding

Participants and providers will be blinded to study drug allocation as all study drug will be prepared by the pharmacist and placed into numbered drug bottles.

Privacy protection

Participant privacy is another ethical concern in this study. Participants may have people with access to their cell phones who do not know about the pregnancy or abortion. Compromising a woman's privacy about this matter could put her at risk depending on her life situation. To prevent this, I plan to use generic language that does not identify the context of the woman's care. Women will be counseled regarding their ability to rescind their participation at any point. Below is the verbatim content of each text message that will be sent to participants. These text messages will be sent in order, with a programmed one-minute interval between each question:

1. "What is your current pain level on a scale of 0-10? (Zero is no pain and ten is the worst pain imaginable)"
2. "How many pills of ibuprofen have you taken since the last text?"
3. "How many pills of acetaminophen with codeine have you taken since the last text?"
4. "Do you feel more dizzy than usual?"
5. "Do you feel more tired than usual?"

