reviewed. Physician investigators will assess for causality or relatedness of the adverse experience to the study.

- In accordance with UC Davis institutional review board (IRB) reporting policy, AEs will be reported at annual IRB renewal submission. SAEs that are unanticipated and thought to be related to the study (thereby placing research subjects at higher risk of harm than originally thought) will be reported to the IRB by the principal investigator within five days of becoming aware of the event.
- The study will be reviewed semimonthly at the Family Planning division research meeting, which includes all research staff. Any concerns regarding individual or trends in AEs will prompt further review of the study and consideration of study termination.
- Study allocation will remain concealed except in a scenario in which revealing allocation is clinically important for the participant's management

11) Withdrawal of Subjects

Based on the safety of existing research on both gabapentin for peri-procedure pain and an existing abortion-related study using text messaging of subjects, we do not anticipate frequent circumstances for participant withdrawal. There are both investigator and participant-initiated modes for subject withdrawal. Participants will be withdrawn from the study pending investigator review of AE that warrants removal or any SAE (see Section 10). Participants will be counseled at enrollment about how to withdrawal themselves from the study for any reason. If a participant is withdrawn from the study, no further data will be collected. We will inquire about the reason for withdrawal so we can monitor for AE/SAE.

12) Risks to Subjects

There are two primary categories of risk in this study:

1. *Study medication risk (Gabapentin):*

As noted in Section 7, Gabapentin is a safe, well tolerated medication that is an established agent of interest for peri-procedure analgesia. Contraindications and medication interactions are few. This study will be monitoring for the more common side effects that can happen (though not frequently in prior studies), including increased self-reported sedation and dizziness from baseline.[25]

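### Tolerability of the home dose rests on one next-day symptom item with no stated recall period, so overnight sedation or dizziness may go unrecorded

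*Combined protocol and SAP*

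**What the plan says.** All references are to the combined protocol and SAP.

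- **Symptom schedule (section 7, steps 3, 6, 9 and 10).** Sedation and dizziness are recorded at baseline, five minutes after insertion, by text, and on pre-operative admission the next day. On the texts: "Participants will be contacted via text message at 2, 4, and 8 hours after dilator insertion". No later text is planned.
- **Home dose (section 7, step 7a).** "One additional study medication (Gabapentin 600 mg or placebo) to take at home 8 hours after the initial dose".
- **Home dose (section 7, step 7c).** The form handed to participants contains "a reminder to take the home dose of their assigned study medication at 8 hours after dilator insertion (exact time will be written out").
- **The 8 hour text (section 7, step 9b).** It carries the "Reminder to take the assigned study medication (at 8 hours only"). The symptom questions in the texts are in the present tense, for example "Do you feel more dizzy than usual", whereas the analgesic questions ask about the time since the previous text.
- **Pre-operative assessment (section 7, step 10).** It covers the current pain score, "additional analgesic use since 8 hour text message contact, and presence of symptoms (sedation and dizziness"). Section 2 describes this visit as the final assessment of pain, side effects and analgesic use.
- **What is to be monitored (section 12).** The common side effects are followed, "including increased self-reported sedation and dizziness from baseline", and the frequency of reported side effects is to be watched closely.
- **General safety (section 10).** Safety data are collected throughout, participants are asked about side effects, and adverse events are logged. No separate timetable or questionnaire is given.

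**The concern.** The trial tests a repeated-dose regimen, and section 12 names sedation and dizziness as the side effects it will monitor. The first dose is followed by symptom questions at five minutes and at 2, 4 and 8 hours after insertion. The home dose, taken unsupervised with acetaminophen/codeine available, is followed by one item on the next day, and that item has no stated recall period.

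If the item is asked as current status, a woman who was dizzy or sedated in the evening or night and felt normal at admission would be recorded as having no symptoms. The by-arm symptom data would then say little about the hours soon after the second dose. Section 7 (Study drug) describes the effects of interest in gabapentin-naive perioperative patients as immediate ones, and a next-day snapshot is poorly placed to catch those. A later statement on the tolerability of the two-dose regimen would have thin support for its second half.

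**Working it through.** The plan states no figure on this point, so the check sets the dosing and assessment schedules side by side.

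**Step 1. Each symptom assessment against the home dose.** Step 7a counts 8 hours from the first dose, which is taken before insertion (section 7, steps 4 and 5). Step 7c counts 8 hours from insertion. Let *d* be the time from first dose to insertion; the documents do not give it.

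| Symptom assessment | If home dose follows 7a | If home dose follows 7c |
|---|---|---|
| Baseline, 5 min, 2 h, 4 h | before | before |
| 8 h text | *d* after the dose is due | at the time the dose is due |
| Pre-operative admission | after | after |

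Under either step, the 8 hour answer comes too close to the home dose to describe its effects. Scheduled symptom assessments clearly after the home dose: 1. Scheduled contacts between the 8 hour text and admission: 0.

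**Step 2. Share of study drug concerned.** The gabapentin arm takes 2 × 600 = 1,200 mg, and the home dose is 600 / 1,200 = one half.

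**Step 3. Length of the unsampled interval.** Section 7 says only that the D&E is on the following day. Assume insertion between 09:00 and 15:00 and arrival between 06:00 and 12:00. With the home dose at 8 hours after insertion:

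gap = 24 + arrival − (insertion + 8)

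- Shortest: 24 + 6 − (15 + 8) = 7 h
- Middle: 24 + 9 − (12 + 8) = 13 h
- Longest: 24 + 12 − (9 + 8) = 19 h

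Under step 7a, the time from home dose to admission is longer by *d*.

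**Step 4. How step 10 is most naturally read.** One sentence holds three items with three time frames: pain is current, analgesic use runs from the 8 hour text, and symptoms are recorded as present or not, with no period. Step 9b uses the same description for the texts, where the actual questions ask how the participant feels now. The analgesic item shows that a look-back was written where one was wanted. Current status is therefore the better-supported reading of the symptom item, but it remains an inference, because the wording of the pre-operative interview is not given.

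**The case against.** The strongest reply is that the pre-operative visit is itself a planned side-effect assessment after the home dose, and section 2 calls it the final one. A reader might infer from the schedule that no symptom question follows the second dose, that its tolerability is not measured, or that the side-effect comparison concerns the first dose only. The documents do not support any of these, because step 10 is a symptom question after the second dose.

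Other points on that side also have force:

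- Step 10 attaches the word current to the pain score and not to symptoms, so a look-back may have been intended. This stands as a reason for less than high confidence. If a look-back was intended, the text should say so, and the remedy is the same.
- Section 10 provides for side-effect questions and adverse event logging throughout, and participants have a 24-hour contact. This stands in part: an overnight event could be reported by that route. But no schedule or instrument is attached, so it would depend largely on women volunteering symptoms and would not give a systematic comparison by arm.
- Section 7 prefers real-time answers to diary-type reporting of pain, and a look-back item relies on memory across a night when many participants will be asleep. Tiredness in particular may be hard to interpret. This stands as a cost of the fix.
- The hypothesis concerns pain at 8 hours, and no analysis specific to the second dose is planned. This stands and limits the severity.

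**Conclusion.** The point holds in limited form. Second-dose tolerability rests on one next-day item with no stated recall period, and no contact is scheduled in between. Transient sedation or dizziness after the home dose may therefore be missed in the comparison between arms. Confidence is moderate, because the conclusion depends on reading step 10 as current status.

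Its size is one half of the gabapentin given and an unsampled interval of about 7 to 19 hours, the latter resting wholly on the assumed clock times. The outcome affected is secondary; this point does not touch the 8 hour pain outcome.

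Two further inferences are tempting and should not be drawn. One is that symptoms must have cleared by admission because section 7 mentions dosing every eight hours: that interval refers to starting long-term treatment at 300 mg and is not a duration of effect for 600 mg. The other is a stated loss of power for a difference in dizziness: the documents give neither event rates by arm nor the share of episodes that would persist to admission, so no such figure can be derived from them.

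Separately, steps 7a ("to take at home 8 hours after the initial dose") and 7c (8 hours after insertion) give different times for the home dose and must be reconciled. This review does not say which is right.

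**What to change.** In section 7, step 10, keep the record of current symptoms and add two yes/no items with the same look-back as the analgesic item: since the 8-hour text, has the participant felt dizzier than usual, and has she felt more tired than usual. Keep the terms close to those of the text questions so that the answers can be set beside the earlier rounds. In section 8 (Statistical Analysis), state that these two items will be reported by arm as the tolerability data after the home dose, separately from the 2, 4 and 8 hour data. Reconcile steps 7a and 7c.

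The cost is two questions and one line on the data form at an interview already held. The drawback is overnight recall instead of a real-time answer. The information cannot be recovered for women already interviewed without these items, so any report should state how symptoms were asked at that visit and the limit this puts on conclusions about the second dose.

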Multimodal pain management has become an area of interest across many procedural fields. Though no data exists regarding current pain management strategies for pain after dilator insertion, anecdotal experience includes recommending over-the-counter analgesics (e.g., acetaminophen and ibuprofen) or oral narcotics. Adjunctive analgesic medications have been explored within Obstetrics and Gynecology for pain management, primarily in the context of Cesarean delivery and abdominal hysterectomy. Gabapentin is one such agent which has both analgesic and antiepileptic properties and few contraindications. [6] Use of this agent, as compared to similar drugs such as pregabalin, is appealing due to its low cost. When considering commonly studied perioperative dosing, gabapentin can be purchased for as low as \$0.24 per 600 mg dose whereas pregabalin is \$14 per 150 mg dose. [7-12] Studies regarding preoperative use of gabapentin in abdominal hysterectomy have demonstrated decreased post-operative narcotic use, decreased nausea and vomiting, and increased patient satisfaction. [8, 13-17] Reports regarding side effects such as sedation are varied. [8, 13-17] Data regarding preoperative gabapentin use and post-operative Cesarean delivery pain is more limited and less consistent. [7, 9, 18, 19] The heterogeneity of gabapentin dosing and overall pain regimen along with study design limitations make these data challenging to generalize to abortion procedures

Ultimately, studies regarding gabapentin for pain relief in abdominal hysterectomy and Cesarean delivery do not serve as good proxies for using gabapentin during abortion care. The pain experience of laparotomy, which is confounded by various regimens of regional and general anesthesia, is different than that of dilator insertion and subsequent D&E. Recent projects by family planning fellows are evaluating the use of gabapentin for medical and surgical abortion in the first trimester. We propose a study to evaluate the effect of gabapentin on the pain experienced between dilator insertion and D&E. I believe this treatment will be beneficial to patients and my findings could be used to create a pain regimen that could encompass both cervical preparation and D&E. Since women will be outside of the healthcare setting for most of their dilator experience, I plan to use short messaging service (SMS; text message) to allow women to communicate pain evaluation and analgesic use in real time.

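### The at-home texts ask about only two analgesics, so they do not deliver the analgesic inventory the protocol promises, and their recall window is ambiguous

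*Combined protocol and SAP*

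**What the plan says.** Step 9 of Section 7 (Procedures Involved) sets the schedule: "Participants will be contacted via text message at 2, 4, and 8 hours after dilator insertion". Step 9b lists the content of each contact, including "Inventory of analgesic use since last contact". Section 2 (Objectives) likewise says that additional analgesic use at home will be captured by text.

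The subsection on privacy protection in Section 7 then fixes the wording: "Below is the verbatim content of each text message that will be sent to participants". Two of the five messages concern analgesics: "How many pills of ibuprofen have you taken since the last text" and "How many pills of acetaminophen with codeine have you taken since the last text". The other three cover pain, dizziness and tiredness. The messages go out in order, "with a programmed one-minute interval between each question". Participants are told in advance how many texts to expect, when, and on what general topics, but they are not shown the wording.

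Step 7b says what women go home with: "Standard prescriptions for acetaminophen 300 mg/codeine 30 mg and ibuprofen 800 mg to take as needed". Section 3 (Background) notes for the field generally that "anecdotal experience includes recommending over-the-counter analgesics (e.g., acetaminophen and ibuprofen) or oral narcotics". Step 10 adds a broader analgesic question on arrival for the procedure, limited to the time after the 8-hour contact.

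**The concern.** The content list and the instrument do not agree. The list calls for an inventory; the instrument asks about two named products. Anything else taken in the first 8 hours has no field at any contact.

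Two lesser weaknesses sit in the same items. The recall period is tied to the last text, although each question follows another text by one minute. The answer is a number of pills with no strength attached.

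As-needed analgesics are open to both arms and can move the 8-hour pain score, which is the time point in the study hypothesis. Equal pain with less supplemental analgesia means something different from equal pain with the same amount. If use before 8 hours is recorded incompletely, the trial is less able to tell these apart.

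**Working it through.** The plan states no figure for this point, so there is none to reproduce. The check sets the promised content beside the wording and works out what each item can record.

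**1. Coverage.** Inputs: step 9b (promised content), the message wording under privacy protection, step 10 (pre-operative question), step 7b (prescribed products).

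| Product taken | Up to the 8-hour contact | After the 8-hour contact |
|---|---|---|
| Prescribed ibuprofen | Item 2; count × 800 mg | Step 10 |
| Ibuprofen of another strength | Item 2; mg unknown | Step 10 |
| Prescribed acetaminophen with codeine | Item 3; count × 300 mg/30 mg | Step 10 |
| Plain acetaminophen | No item | Step 10 |
| Any other pain reliever | No item | Step 10 |

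A woman in either of the last two rows who answers exactly what is asked replies 0 to item 2 and 0 to item 3. Step 10 does not reach back to recover that use. Nothing in the documents restricts participants to the two prescribed products. This result needs no assumption about how the questions are read.

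**2. Recall window.** Inputs: contacts at 2, 4 and 8 hours; messages one minute apart; a baseline text sent before the woman leaves the clinic.

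- Intended windows: about 2 h (from the baseline text), then 4 − 2 = 2 h, then 8 − 4 = 4 h. Together these are about 8 h, or 480 minutes.
- Strictly literal windows: when item 2 arrives, the last text is item 1, one minute earlier; when item 3 arrives, it is item 2, one minute earlier. Over three rounds each item would cover 3 × 1 = 3 minutes, and 3/480 ≈ 0.6% of the period.

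The phrase is also unclear after a missed round: it could mean the last text sent or the last one answered. No explanation of the phrase to participants is described.

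**3. Strength.** If only prescribed tablets are taken, one ibuprofen pill is 800 mg and the count converts exactly. The documents give no other ibuprofen strength. Assuming tablets anywhere from 200 to 800 mg, a reply of 2 would mean between 2 × 200 = 400 mg and 2 × 800 = 1,600 mg. That is the range for one reply, not an estimate of error across the study.

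**4. Direction of the effect.** Let D be the true difference between arms in mean use, and suppose the same fraction g of use goes unrecorded in each arm. The recorded difference is then (1 − g) × D, which is smaller than D for any g above 0. Identical wording and blinding make a similar g in both arms plausible, although this is not guaranteed. The documents give no value for g, so the size cannot be calculated.

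**The case against.** The case on the other side has real force.

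- **Strength.** Every woman is prescribed one strength of each product, and the two items name exactly those products. This largely answers the strength point. A reader might infer a four-fold dose error from 800/200 = 4. That figure is a worst case for a single dose, rests on an assumed 200 mg tablet, and comes with no rate of substitution in the documents.
- **Over-the-counter use.** A reader might infer that such use is usual at this clinic. Section 3 reports only anecdotal experience in the field and says there are no data on current strategies. Use outside the prescriptions is foreseeable, but its frequency is unknown.
- **Window.** Women know the contact times and are paid per round, so many will take the last text to mean the previous round. A reader might infer that a set share, say 10% to 30%, will answer zero. No such share is in the documents, and the wording alone does not show that answers will be wrong. The ambiguity remains.
- **Importance.** Analgesic use is not the primary outcome, and the Statistical Analysis paragraph in Section 8 specifies no adjusted or dose-based analysis of it. A reader might infer that the primary comparison is compromised or that nothing can be said about supplemental analgesia. Neither follows: these items do not enter the pain score, and reported use of the two prescribed products stays usable. A yes/no comparison of ibuprofen use does not depend on tablet strength.

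None of this answers the missing products. Short generic texts do protect privacy, but a question about other pain medicine is equally generic.

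**Conclusion.** The point holds in a limited form. The message wording does not deliver the protocol's own stated content, because analgesics other than the two named are unrecorded up to 8 hours. The unclear recall period is a real but lesser defect, and the missing strength matters only for tablets other than those prescribed.

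The consequence is confined to a non-primary co-intervention measure used to interpret the 8-hour pain score. The most likely effect is under-counting in both arms, with any true difference in use diluted. This rests on two assumptions: that some women take other products, and that the loss is similar in the two arms. No size can be derived from the documents. The change is worth making because it is cheap and brings the instrument into line with the plan.

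**What to change.** - Keep items 2 and 3 as two separate questions, each answered with a single number.
- In both, replace the reference to the last text with *since the last set of questions*, or with the clock time of the previous scheduled contact. The 2-hour round has no earlier set of questions, so a clock time is clearer there.
- Add one separate generic item: *Have you taken any other pain medicine since then? If yes, name, strength and number of pills.* It should not be merged into item 3, where a bare reply of 2 could not be interpreted.
- Update the payment rule under Participant Compensation, which depends on answering all five messages, so that it refers to six.
- At the pre-operative interview, ask about any other pain medicine, and any non-prescribed ibuprofen with its strength, over the whole interval since insertion.

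The cost is one more text per round: 3 × 6 = 18 messages instead of 3 × 5 = 15, plus edits to the templates and the interview form. Treatment, visits and sample size are unchanged, and nothing in the new wording identifies the context of care. This version is dated 01/11/2018, and Section 5 gives February 2017 to January 2018 as the enrolment goal. If enrolment is already under way, data collected before and after the change must be flagged as coming from two versions of the questions.
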